2.2 IND Agent

ONC201 is a first-in-class small molecule (imipridone) selective DRD2 antagonist that functions by activating the integrated stress response (ISR) in tumors cells, leading to downstream anticancer effects that include inactivation of prosurvival Akt and ERK signaling along with induction and activation of the TRAIL apoptosis pathway (Allen et al., 2013). ONC201 has demonstrated broad spectrum antitumor efficacy in numerous solid and liquid tumor preclinical models, including cell lines and patient samples that are refractory to chemotherapy and targeted therapies. This is independent of mutations in genes such as p53, KRAS, Raf, EGFR. ONC201 is orally available, has demonstrated a wide therapeutic window preclinically, is highly stable and water soluble, and is able to penetrate the blood-brain barrier. ONC201 does not induce cell death in normal cells. In vivo studies indicate that the safety margin (ratio of therapeutic dose to lowest dose with a mild adverse event) of ONC201 is at least 10-fold in rats and dogs in GLP toxicology studies. ONC201 has demonstrated antitumor activity in high grade gliomas, as demonstrated use in *in vitro*, ex vivo, and *in vivo* models. In early clinical studies ONC201 has been well tolerated. The safety profile along with its mechanism of action makes ONC201 suited to address gliomas by potentially circumventing limitations of available therapies.

For complete details of ONC201, please refer to the Investigator's Brochure.

2.2.1 Preclinical Efficacy in High Grade Glioma

ONC201 induces cell death in a broad spectrum of tumor types harboring diverse mutations in genes such as p53, KRAS, Raf, EGFR, and others, that results in resistance to chemotherapies and targeted agents. ONC201 induces caspase-mediated apoptosis in cancer cell lines and exhibits broad-spectrum cytotoxicity *in vitro*. ONC201 exhibits promising anticancer activity that has been demonstrated in multiple malignancies in preclinical models that include subcutaneous, orthotopic, and transgenic models, in addition to a large body of *in vitro* data that demonstrate its cytotoxic effects and its mechanism of action. ONC201 displays single agent antitumor effects in subcutaneous and orthotopic colon cancer, subcutaneous triple negative breast cancer, subcutaneous non-small cell lung cancer, subcutaneous and orthotopic intracranial glioblastoma, and immunocompetent lymphoma transgenic mouse models. ONC201 also cooperates extensively with paclitaxel, docetaxel, and bevacizumab. We have chosen to target GBM for ONC201 development given the wealth of positive preclinical information that was generated with the study drug.

In addition to potent *in vitro* activity, ONC201 shrinks temozolomide-resistant GBM xenografts (Figure 1A) and prolongs the survival of mice with orthotopic xenografts as a monoagent and in combination with bevacizumab (Figure 1B). Corroborating observations by other investigators have demonstrated the compelling monoagent efficacy of ONC201 in radio- and chemo-resistant GBM cell lines. Other studies have demonstrated highly potent cytotoxic activity with ONC201 in three-dimensional neurosphere cultures of newly diagnosed and recurrent GBM patient samples.

[figure not shown]

Figure 1 (A) Relative tumor size (compared to day 0) in a subcutaneous xenograft of T98G in mice treated with a single dose of vehicle, ONC201 (30 mg/kg,orally), or bevacizumab (10 mg/kg, iv) onday 0 (n = 8). (B) Overall survival of mice harboring SF767 intracranial tumors treated with a single oral dose of vehicle (n = 8), ONC201(25 mg/kg, n = 7),bevacizumab

[figure not shown]

Figure 2 GI50 GBM cell lines at 72 hours after treatment with ONC201 or DMSO (n = 3).

Figure 3 T98G TMZ-resistant and radioresistant GBM cells following treatment with ONC201 at indicated concentrations (72 hr).

ONC201 demonstrates p53-independent activity in human GBM cell lines in the low micromolar range (Figure 2). ONC201 exerts a strong cytotoxic effect, unlike temozolomide, against tumor cells isolated from a freshly resected GBM

with an oligodendroglial component that was previously resected and irradiated. Observations by external investigators demonstrate the compelling monoagent efficacy of ONC201 in radio- and chemo-resistant GBM cell lines (Figure 3) and 3D neurosphere cultures (Figure 4).

[figure not shown]

Figure 4 ONC201 kills newly diagnosed and recurrent GBM neurospheres. Cell viability of neurosphere GBM cultures following

2.2.2 Mechanism of Action

ONC201 is a selective antagonist of the G protein- coupled receptor DRD2 that was identified through a phenotypic screen as a p53- independent small molecule inducer of TRAIL gene transcription in tumor cells. A series of gene expression profiling and cell signaling investigations have unraveled signaling pathways that are engaged in tumor cells following ONC201 treatment.

Downstream of target engagement, ONC201 activates the integrated stress response

[figure not shown]

Figure 5 Proposed model of ONC201 mechanism of action in

(ISR), which is the same signaling pathway activated by ER stress-inducing compounds, such as proteasome inhibitors (e.g. bortezomib). When the ISR is activated by ER stress-inducing compounds, the pathway is often referred to as the ER stress response. ONC201 causes an early-stage increase in the phosphorylation of eIF2-alpha at serine 51, which results in attenuation of protein translation and upregulation of the transcription factor ATF4 (Figure 5). ATF4 upregulates CHOP, which is also a transcription factor that regulates several apoptosis-related genes such as the TRAIL-receptor DR5. ATF4 and CHOP upregulate expression of TRB3, which interacts directly with Akt to decrease its kinase activity. TRB3 also

serves as a scaffold protein in the MAPK signaling pathway that can negatively regulate this pathway. Decreased levels of phospho-MEK, -ERK, and -Akt have been documented in response to ONC201. The decreased ERK and Akt kinase activity results in less phosphorylated Foxo3a, which is a transcription factor that regulates both the TRAIL and DR5 genes. Dephosphorylated Foxo3a undergoes nuclear translocation and activation in response to ONC201.

In summary, ONC201 inhibits DRD2 to cause downstream activation of ATF4, which causes induction of genes that lead to apoptosis. DRD2 antagonism also downregulates Akt and ERK activity to cooperatively induce complementary downstream apoptotic effects. ONC201 may not activate eIF2-alpha through PERK. This distinct mechanism may explain the lack of cross-resistance between ONC201 and other ER stress-inducing agents such as bortezomib. In addition, ONC201 has enhanced antitumor efficacy in combination with bortezomib that may be explained by engaging parallel stimuli that lead to an enhanced activation of the ISR in tumor cells.

2.2.3 Nonclinical Safety/Toxicology Studies in Animals

In rats and dogs, ONC201 was better tolerated when administered orally, compared to intravenously. In rat non-GLP studies, the No-Observed Adverse Effect Level (NOAEL) was 225 mg/kg with oral administration compared to 100 mg/kg with a 2-hour infusion and 50 mg/kg with a 30 minutes infusion. Non-GLP clinical observations in rodents included decreased activity, altered gait, and mortality. In dog non-GLP studies, the NOAEL dose was at least 120 mg/kg with oral administration and clinical observations were limited to emesis and changes in fecal consistency. The non-GLP studies only evaluated clinical observations, weight gain, food consumption and gross findings at necropsy. In general, the toxicology/safety studies indicate that the acute toxicities associated with ONC201 are limited to the day of administration and are reversible.

In dog GLP studies, the NOAEL was at least 42 mg/kg. Observations were limited to decreased activity, decreased food consumption, emesis, salivation, and/or soft, loose or mucous feces. In rat GLP studies, the NOAEL was at least 125 mg/kg. Observations included decreased activity, decreased food consumption, decreased body weight, and abnormal stance and gait. Minor changes in serum chemistries were noted, largely in the 225 mg/kg rats that included a slight increase in cholesterol and chloride. The significance of these findings is unknown as other clinical chemistry and histology did not corroborate this observation (e.g. liver findings). Rats receiving 125 or 225 mg/kg ONC201 had mild edema and inflammation that was primarily submucosal in the stomach and was completely resolved by day 19.

2.2.3.1 Non-GLP Safety Studies

Non-GLP studies were conducted in rats and dogs to assess clinical observations and body weight with ONC201.

Non-GLP toxicology studies in rats

The ability of rats to tolerate ONC201 by intravenous administration was explored as a function of infusion time. Clinical observations with intravenous administration included decreased activity, salivation, abnormal gait and stance, labored respiration, pale skin, nasal discharge, prostration during the dose, mild body twitching, and red discharge from the mouth.

The NOAEL following administration of ONC201 to Sprague-Dawley rats by a 30-minute intravenous infusion was 50 mg/kg. The NOAEL following administration of ONC201 to Sprague-Dawley rats by a 2-hour intravenous infusion was 100 mg/kg. Administration of 100 mg/kg ONC201 by intravenous infusion over 30 minutes resulted in the death of one male rat. Administration of 200 mg/kg ONC201 by a 2-hour infusion resulted in the death of both animals during the infusion period. Following these observations, the tolerance of oral ONC201 was explored given the potential to lower acute toxicity by lowering Cmax. Clinical observations with oral exaggerated doses of ONC201 included decreased activity, abnormal gait and stance, prostration, irregular respiration, moderate twitching, red discharge on the muzzle, scant feces, hunched posture, not eating, pilerection, and skin cold to touch. The NOAEL following administration of ONC201 to Sprague-Dawley rats by oral gavage was 225 mg/kg.

Non-GLP toxicology studies in dogs

In parallel to non-GLP toxicology studies in rats, the ability of beagle dogs to tolerate ONC201 was explored. No deaths were observed at any doses in dogs. The NOAEL following the 30-minute intravenous infusion of ONC201 to beagle dogs is considered to be at least 33.3 mg/kg. The 2 hour-intravenous infusion of 16.7 mg/kg ONC201 was not associated with any clinical signs of toxicity. Therefore, the NOAEL following a 2 hour-intravenous infusion of ONC201 to beagle dogs is considered to be greater than 16.7 mg/kg, though higher doses were not explored as the oral route was selected for further development based on observations in rats. The NOAEL with oral ONC201 was considered to be at least 120 mg/kg in dogs. Clinical observations at doses of 66.7 to 120 mg/kg were limited to emesis and changes in fecal consistency.

2.2.3.2 *GLP Toxicology and Safety Studies*

Single Dose Oral Toxicity Study in Dogs (GLP)

A GLP study was performed to evaluate the toxicity and toxicokinetics of ONC201 following a single oral dose to Beagle dogs followed by a 2-day or an 18-day recovery period. Dogs received a single dose of 0, 4.2, 42, or 120 mg/kg by oral gavage. There was no mortality observed in this study. There were no definitive ONC201-related effects on group mean body weight or body weight gain, ECG rhythm or morphology, mean heart rate or arterial blood pressure, urinalysis, hematology parameters, coagulation parameters, clinical chemistry parameters, erythrocyte morphology, gross findings on necropsy, changes in absolute or organ to body or organ to brain weights.

Although not statistically significant, there were some dose-related decreases in group mean food consumption for the first week following dosing. The 120 mg/kg females had statistically significantly decreased group mean food consumption compared to the vehicle control group on Days 14, 15 and 18. There were no clinical signs of toxicity noted following a single dose of 4.2 mg/kg ONC201. At a dose of 42 mg/kg and 120 mg/kg, some dogs had clinical observations at approximately 1 hour post-dose including decreased activity, emesis, salivation, and/or soft, loose or mucous feces. Of uncertain relationship to ONC201 administration was the unusual finding of mononuclear cell inflammation in the blood vessels of the brain, which was multifocal and mild in one high dose female at Day 3, multifocal and minimal in one high dose female at Day 19, and minimal and focal in one control female at Day 19. Similar findings were not noted in any male animal.

Based on the results of this study, the NOAEL following oral administration of ONC201 at single doses of 4.2, 42 or 120 mg/kg to Beagle dogs is considered to be at least 42 mg/kg.

Single Dose Oral Toxicity and Toxicokinetic Study in Rats with a 19-Day Recovery and a 30-Minute Intravenous Infusion Toxicokinetic Arm(GLP) A GLP study was performed to evaluate the toxicity of ONC201 following a single oral dose in Sprague-Dawley rats with necropsy after a 2-day or an 18-day recovery period. Rats received 0, 12.5, 125, or 125 mg/kg ONC201 by oral gavage.

There was no mortality observed in this study. There were no definitive ONC201-related effects on coagulation parameters, clinical chemistry parameters, gross findings at necropsy. There were no clinical signs of toxicity noted at single doses up to 125 mg/kg ONC201. There were no ONC201-related statistically significant changes in hematology parameters or clinical chemistries outside of the historical control range for these values.

At a dose of 225 mg/kg, clinical signs of toxicity were limited on the day of dose administration to one out of twenty males and one out of twenty females that showed signs of decreased activity and abnormal gait and stance. The male was also noted to have increased respiration. All were normal by Day 2. No ONC201 related changes were noted during the functional observational battery (CNS activity) performed on Day 1 between 1 and 2 hr post-dose with the exception of one 225 mg/kg female noted as having decreased activity. A statistically significant decrease in group mean body weight gain was noted on Day 7 for the 225 mg/kg males. A statistically significant decrease in group mean food consumption was noted on Day 7 for the 225 mg/kg males.

On Day 3 the 225 mg/kg females also had increased glucose, cholesterol, sodium and chloride. Sodium and chloride were statistically significantly

increased for the 125 mg/kg females. Only cholesterol and chloride were outside historical control ranges for this laboratory on day 19. As the increase in cholesterol was only noted for the females and no corresponding liver findings were observed, the significance of this finding is unknown. Though within normal historical control values for these laboratories, chloride remained increased for the 225 mg/kg males while cholesterol remained increased for the 225 mg/kg females.

Changes in brain and liver weights were noted but did not occur in a dose-dependent manner and no microscopic changes were noted for in these organs for the high dose females. These changes were considered incidental and unrelated to treatment. At the Day 3 necropsy, ONC201- related minimal to mild edema and/or mixed cell inflammation was present in the non-glandular stomach of 225 mg/kg males and females. This edema and inflammation was primarily submucosal, although in some animals the inflammation involved the serosa or mesentery. Two males and one female had minimal focal ulceration of the overlying squamous epithelium. Similar stomach findings were seen in 125 mg/kg animals, with a lower incidence than in 225 mg/kg. There was complete resolution of all stomach lesions at the Day 19 necropsy, indicating full recovery.

Based on the results of this study, the NOAEL following oral administration of ONC201 at single doses of 12.5, 125 or 225 mg/kg to Sprague-Dawley rats is considered to be at least 125 mg/kg.

Evaluation of the Effect of ONC201 Dihydrochloride on Respiratory Function Following Single-Dose Administration in Rats (GLP)

A GLP study was performed to determine the potential effects of ONC201 dihydrochloride on respiratory function in rats following a single oral gavage administration. Twenty-four (6/group) male rats received 0, 12.5, 125, or 225 mg/kg ONC201 by oral gavage and were monitored in plethysmographic chambers. The oral administration of ONC201 dihydrochloride at 12.5 and 125 mg/kg did not induce any biologically relevant effects on respiratory rate, tidal volume or minute volume in conscious male rats. A marginal to moderate transient decrease in respiratory rate and minute volume was observed following the oral administration of ONC201 dihydrochloride at 225 mg/kg, which resolved by 2 hours.

2.2.4 Pharmacokinetic Studies

2.2.4.1 Pharmacokinetic Studies in Animals

The measured half-life of ONC201 in mice is \sim 6 hours with intravenous administration as measured by an HPLC-UV assay.

In rats, exposure to ONC201 was dose-dependent and approximately dose-proportional. Exposure to ONC201 was slightly greater in female rats after a single oral gavage dose. Plasma $T_{1/2,e}$ ranged from 2.3 to 8.4 hours in 7 of 8

profiles. Clearance ranged from 7.5 to 23.5 L/hr/kg in 7 of 8 profiles. Volume of distribution ranged from ~49 to ~103 L/kg in 6 of 8 profiles.

[figure not shown]
In dogs, exposure to ONC201 following oral gavage dosing at 4.2, 42, and 120 mg/kg ONC201 was dose-dependent and increased with greater ONC201 dose levels. Exposure to ONC201 was similar in male and female dogs with the observation that all mean male Cmax and AUC values were slightly greater than those corresponding female values.

Elimination of ONC201 from plasma was similar between the mid and high dose levels; mean $T_{1/2,e}$ ranged from 4.6 to 7.8 hours. Mean $T_{1/2,e}$ following the low dose of 4.2 mg/kg was ~1 hour [the half-life determined for dogs in the low dose group may represent more of a distribution phase half-life rather than the terminal plasma elimination half-life]. Overall elimination of ONC201 was greater following the low dose.

2.2.4.2 Pharmacokinetic Studies in Humans

In a Phase I dose escalation clinical trial of ONC201 in advanced solid tumors, the pharmacokinetics of single agent ONC201 was determined by LC-MS-MS analysis of plasma collected in the first cycle of therapy within 21 days of drug administration (Fig 6; Table 2.1). Trends of increasing exposure with dose were consistent with dose proportionality. Patients receiving 625mg ONC201 exhibited a mean half-life of 11.3 hours and achieved a Cmax of 3.6 ug/mL (~9.3 uM), which occurred at1.8 hours following administration (Tmax). The mean volume of distribution was 369 L, consistent with a large distributive volume. Mean AUC was 37.7 h.µg/mL and mean CL/F was 25.2 L/h. Generally, CL/F was observed to be variable but consistent across all dose groups. There were no apparent relationships between drug CL/F and patient sex and age. Noticeable, shallow trends were observed with patient weight and BSA. An overall increase in CL/F was observed as weight and BSA increased. Although a slight upward trend was observed, there was no strong correlation between CL/F and CLCR.

Figure 6 ONC201 pharmacokinetic parameters

Stronger correlations were observed with the distributive volume estimate and patient weight and BSA. An increase in volume of distribution was observed with increasing patient weight or BSA, as expected. Trends of

## 1. Introduction

This abbreviated Statistical Analysis Plan (SAP) describes the statistical analyses to be conducted for the Study ONC013. For simplicity, reference is made to existing Integrated Summary of Safety (ISS) and Integrated Summary of Efficacy (ISE) SAPs when approaches are the same.

Study ONC013 is a Phase II, open-label, multi-center clinical trial of ONC201 in adult recurrent glioma with two arms. All subjects receive oral ONC201 at 625 mg every week. All subjects remain on study until progressive disease, unacceptable toxicity or withdrawal of consent. For other study details, refer to the study protocol.

## 2. General Conventions

The All Treated Analysis Set includes all patients who receive at least one dose of ONC201. This will be used for all analyses.

Unless otherwise specified, continuous variables will be summarized using descriptive statistics [number of observations, mean, standard deviation (SD), median, 1st (Q1) and 3rd (Q3) quartiles, minimum and maximum]. Categorical variables will be summarized as number (percent) of patients.

Day 1 is defined as the date of the first dose of study drug. For events that occur on or after Day 1, study day is defined as (date of event - date of Day 1 + 1). For events that occur prior to Day 1, study day is defined as (date of event - date of Day 1). There is no Day 0. Baseline is defined as the last observed measurement on or before the date of the first dose of study drug.

In general, other than for partial dates, missing data will not be imputed and will be treated as missing. Unless otherwise specified, partial dates will be imputed using the following rules:

- If year is missing, do not impute.
- If only day is missing, impute day as 1st of the month for start dates, end of the month for end dates, and 15th of the month for other dates.
- If day and month are missing, impute as January 1st for start dates, December 31st for end dates, and July 1st for other dates.

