## 3. Analyses

All analyses will be presented by Arm and for All Patients. Otherwise, specified patient disposition, study drug usage, prior/concomitant/post-ONC201 medications, demographic and baseline characteristics, adverse events, and laboratories will use methods and summaries defined in the ISS SAP.

Laboratory boxplots will be presented for all tests with at least 60 patients having numeric baseline results: one plot per test, time on the x-axis, value on the y-axis. The plots will not be broken out by arm (i.e. only the All Patients group). Only Baseline and Cycles 2-12 will be presented. For Cycles 2-12, nominal visits will be used; if multiple values are associated with a visit, the highest value will be used for chemistry tests and lowest value will be used for hematology tests.

The following efficacy analyses will be performed: best overall response, overall response rate, disease control rate, duration of response, progression-free survival, and overall survival. All analyses will be based on the investigator-assessed overall RANO response. Discontinuation of treatment due to progressive disease will also be considered. All analyses, aside from overall survival, will be censored at

the earlier of: (1) last disease assessment or (2) last assessment prior to initiation of other anticancer therapy.

Cycle 1 (2hr, 24hr, 48hr, 72hr) ONC201 plasma concentrations will be summarized descriptively, including geometric mean and %CV. BLQ results will be imputed as zero.

Collected data contributing to presented tables and figures will be listed.

Other analyses specified in the protocol will either not be completed, or will be defined outside the scope of this plan.

Following is a complete list of the tables, figures, and listings to be prepared (with clarifying notes in parentheses).

Number	Description
Table 1.1	Patient Disposition
Table 1.2	Demographics and Baseline Characteristics
Table 1.3	Study Drug Usage
Table 1.4.1	Prior Medications
Table 1.4.2	Concomitant Medications
Table 1.4.3	Post-ONC201 Medications
Table/Figure 2.1	Progression-free Survival
Table/Figure 2.2	Overall Survival
Table 2.3	Response Rate (includes ORR, BOR, and DCR)
Table/Figure 2.4	Duration of Response
Table 3.x.1*	Treatment-emergent Adverse Events (TEAE)
Table 3.x.2*	TEAE Grade 3 and Above
Table 3.x.3*	Serious TEAE
Table 3.x.4*	TEAE Leading to Death
Table 3.x.5*	TEAE Leading to Study Drug Discontinuation, Reduction, or Interruption
Table 3.x.6*	Study Drug Related TEAE

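### The SAP's default for partial start dates has no lower bound: unless the ISS or ISE SAP overrides it, adverse events can be dated before first dose and new therapy before a same-month progression scan (minor, cheap improvement)

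*SAP*

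**What the plan says.** SAP section 2 introduces its date rules with "Unless otherwise specified, partial dates will be imputed using the following rules". A date missing only its day becomes the 1st "of the month for start dates, end of the month for end dates"; a start date missing day and month becomes 1 January. Day 1 is the first dose, and earlier dates get negative study days. No bound is set at Day 1, at the last dose or at a known assessment.

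Two sets of outputs depend on such dates:

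- **Efficacy.** SAP section 3 censors every efficacy analysis except overall survival at the earlier of the last disease assessment and the "last assessment prior to initiation of other anticancer therapy". It adds: "Discontinuation of treatment due to progressive disease will also be considered".
- **Safety.** The adverse event tables are produced twice. By the footnote to the table list, x=1 covers everything after baseline and x=2 stops at the start of other anticancer therapy.

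Other documents may govern. SAP section 1 says that "reference is made to existing Integrated Summary of Safety (ISS) and Integrated Summary of Efficacy (ISE) SAPs when approaches are the same". Section 3 says that adverse events and post-ONC201 medications, among other items, "will use methods and summaries defined in the ISS SAP". The efficacy paragraph of section 3 states its own censoring rule and cites neither integrated SAP.

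**The concern.** Imputing to the 1st always moves a start date to the earliest day of its month. That is harmless until the date is compared with another date in the same month. Two such comparisons matter here.

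- **Adverse event onset against first dose.** An event that began on treatment can receive a negative study day. Whether it then leaves the treatment-emergent tables depends on a definition held in the ISS SAP. It would remain in Listing 3.1.
- **New therapy against the progression scan.** Therapy that followed progression can be dated before it. Read literally, the censoring rule then discards the progression and censors at the previous scan. The same early date removes adverse events from the x=2 tables, although they stay in x=1.

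The PFS error has one direction: an event becomes censoring about 8 weeks earlier, which lengthens PFS and, for a responder, duration of response. PFS at 2 and 6 months and median duration of response are secondary objectives (protocol section 1.3).

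**Working it through.** The plan states no figure on this point, so there is none to reproduce. The date, study-day and censoring rules come from SAP sections 2 and 3, and the 8-week scan interval from protocol section 1.1. Calendar dates, lags, uptake and missingness are assumptions.

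**1. Adverse event example.** Day 1 is 20 March 2018 and true onset 25 March, so the study day is 25 − 20 + 1 = 6. With the day missing, onset becomes 1 March: study day 1 − 20 = −19. With the month also missing it becomes 1 January: study day −78.

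**2. PFS example.** First dose 18 January 2018; scans 15 March (Day 57) and 10 May (Day 113, progression). New therapy truly starts 20 May and is recorded as May 2018, so it is imputed to 1 May. The last assessment before that is 15 March. An event at Day 113 becomes censoring at Day 57, and adverse events from 1 to 19 May leave the x=2 tables.

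**3. How often day-missing dates are misordered.** All 730 dates in the 24 months of 2018-2019 are taken as equally likely.

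*Therapy starting L days after the scan.* In a month of M days, the imputed start precedes the scan for M − L − 1 scan days (zero if negative). For L up to 27 the total is 730 − 24(L + 1).

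| L (days) | Count | Share |
|---|---|---|
| 7 | 730 − 192 = 538 | 74% |
| 14 | 730 − 360 = 370 | 51% |
| 21 | 730 − 528 = 202 | 28% |
| 28 | 8 × 1 + 14 × 2 = 36 | 5% |
| 35 | 0 | 0% |

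(At L = 28, eight 30-day months give one day each and fourteen 31-day months give two.)

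*Adverse event onset spread evenly over the first W days.* For W up to 28 the share dated before Day 1 is 1 − 24 × (W + 1)/2 ÷ 730:

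- W = 7: 1 − 96/730 = 87%
- W = 14: 1 − 180/730 = 75%
- W = 28: 1 − 348/730 = 52%
- W = 56: (28 × 382 + 36 + 14)/(56 × 730) = 10,746/40,880 = 26%
- W = 112: 10,746/81,760 = 13%

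**4. A last-dose floor alone is not enough.** Dosing is weekly ("All subjects receive oral ONC201 at 625 mg every week"). Assume the last dose falls 0 to 6 days before the scan, equally likely. The day after it still precedes the scan in 5 of 7 cases, so the therapy shares fall only to 5/7 of those above: 53%, 36%, 20%, 4% and 0%. In the example, a last dose on 3 May gives a floored start of 4 May, still before 10 May.

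**5. Effect on 6-month PFS.** Simulation: 600 runs, n = 95, exponential PFS with median 60 or 100 days, scans every 56 days, therapy lag uniform over 1-28 or 1-42 days after the scan, Kaplan-Meier at day 183 (14.3% or 31.1% without the error). Rise in percentage points, by share of therapy starts lacking the day:

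| Scenario | 5% | 10% | 20% |
|---|---|---|---|
| All start new therapy, no event rescued (upper bound) | 0.3-0.8 | 0.7-1.5 | 1.4-3.2 |
| 50% uptake, half of lost events rescued | 0.1-0.2 | 0.2-0.4 | 0.3-0.8 |
| 50% uptake, 90% rescued | 0.02-0.04 | 0.03-0.08 | 0.06-0.16 |

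Rescue means that progression recorded as the reason for stopping treatment keeps the event. Adding 28 days to every lag cuts the upper-bound shift at 20% missing to at most 0.01 points.

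**6. Scale.** The binomial standard error √(p(1 − p)/n), at p = 0.143 and 0.311, is 3.6-4.7 points for n = 95, 4.7-6.2 for n = 56 and 5.6-7.4 for n = 39.

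**7. Response rate.** "The All Treated Analysis Set includes all patients who receive at least one dose of ONC201", and that set is used for all analyses, so imputation does not change the denominator. Losing a later progression scan removes no earlier response.

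**The case against.** The strongest objection is that both consequences may be settled in a document not seen. The rule is only a default, the SAP calls itself abbreviated, and adverse events and post-ONC201 medications are delegated to the ISS SAP. The protocol text at hand also stops in section 2.2.4.2. A reader might infer that the plan has no floor and that treatment-emergent events will be lost. The documents do not support that: they show only that this SAP does not state a floor, and its text contains no treatment-emergent definition. The objection is weaker for PFS, because the efficacy paragraph sets its own censoring rule and refers to neither integrated SAP.

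Second, protocol section 1.1 keeps subjects on study until progression is confirmed. If confirmation delays the switch by 28 days or more, the PFS effect nearly vanishes. The confirmation interval is not in the text at hand, so this remains a scenario, but a fair one. Section 1.1 also schedules contact every 30 days (±7) to record new treatment. That should limit partial dates, although contact by telephone, e-mail, fax or mail may still yield only a month.

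Third, the sentence on discontinuation for progression may preserve the event. Its precedence over new-therapy censoring is not stated. It is tempting to give it general precedence, but that would alter PFS censoring for patients with complete dates who truly switched first. The date problem does not justify that.

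Fourth, the adverse event shares apply only to day-missing onsets. Toxicity assessment is continuous on treatment, so these may be few, and no count of affected events can be given.

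**Conclusion.** The point holds conditionally. Followed literally, and absent an override in the ISS or ISE SAP, the default dates some on-treatment adverse events before Day 1 and some post-progression therapy before the progression scan.

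A reader might infer that PFS is materially inflated or that the primary endpoint is biased. Neither is supported. The PFS shift is under 1 point with 50% uptake and half the lost events rescued, and reaches 3.2 points only if every patient switches soon after progression, nothing is rescued and 20% of starts lack the day. It is probably small against sampling error, and near zero if new therapy starts 28 or more days after the scan. Response rate is essentially unaffected; that reasoning is for day-missing dates, and starts known only by year were not sized.

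Every PFS figure rests on assumed inputs, because the documents do not give the frequency of partial dates. Severity is minor; this is a cheap improvement.

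**What to change.** Cite the ISS or ISE clause that already bounds these dates. If there is none, add to SAP section 2:

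1. An imputed adverse event start in the month (or year) of first dose is the later of the imputed date and Day 1, unless a known end date precedes Day 1.
2. For partial dates only, the imputed start of a therapy recorded as post-ONC201 is no earlier than the day after the last ONC201 dose, kept within the recorded month or year. This does not apply to anticancer agents recorded as concomitant with ONC201.
3. Where a partial new-therapy date leaves its order against a documented progression scan in the same recorded month or year ambiguous, count the progression as the event, and report PFS censored the other way as a sensitivity analysis. The rule for complete dates is unchanged.

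In the PFS example, rule 3 counts an event at Day 113, and the sensitivity run censors at Day 57.

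The cost is a few lines of text and code and one PFS run limited to ambiguous dates. There are two downsides:

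- Rule 1 can count a pre-dose event as treatment-emergent. A true onset spread evenly over the 7, 14 or 28 days before first dose shares its month in 87%, 75% or 52% of cases.
- Rule 3 can count a progression after a true switch. A switch 7, 14 or 21 days before the scan shares its month in (730 − 24L)/730 = 77%, 54% or 31% of cases. The sensitivity run shows the effect of this.
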